4.1.1 Dose Escalation Criteria

Term	Percentage
GMOs	95
Organic	85
Natural	80
Artificial	65
Organic	85
Natural	80
Artificial	65
Organic	85
Natural	80
Artificial	65
Organic	85
Natural	80
Artificial	65
Organic	85
Natural	80
Artificial	65

4.2 Start of Study and End of Study

The study period begins when the first participant signs the trial informed consent form (ICF) and ends when the last participant completes the follow-up visits, discontinues from the trial, or is lost to follow-up (i.e., the investigator is unable to contact the participant).

5 STUDY POPULATION

The study population includes adults with moderate-to-severe AD. Eligibility criteria include the following.

5.1 Inclusion Criteria

Participants must fulfil all of the following inclusion criteria for entry into the study:

- 1) Male or female aged ≥ 18 and < 75 years.
- 2) Able to participate and comply with all study procedures and restrictions, and willing to provide written informed consent to participate in the study.
- 3) Diagnosed with AD for [REDACTED], according to the American Academy of Dermatology Consensus diagnostic criteria ([Eichenfield et al. 2014](#)) at the Screening visit.
- 4) Moderate-to-severe AD, defined as:

- a) EASI score ≥ 12 at the Screening visit and ≥ 16 at the Baseline visit
- b) IGA ≥ 3 at the Screening visit and the Baseline visit
- c) BSA $\geq 10\%$ at the Screening visit and the Baseline visit

5) Documented history of inadequate response or lack of tolerability, as assessed by the investigator, to a stable regimen (≥ 4 weeks) of one or more topical treatment, e.g., TCS or TCI before the Screening visit, or for whom topical treatments are otherwise inadvisable.

6) Agree to apply a stable dose of a non-medicated emollient (moisturizer) twice daily at least one week before the Baseline visit and throughout the study.

7) Female participants who are not pregnant or breastfeeding and meet at least one of the following conditions:

- a) Not of childbearing potential as described in [Section 5.3](#).
- b) Of childbearing potential and agrees to use a highly effective method of contraception as described in [Section 5.3](#) consistently from signing of informed consent until 6 months after the last dose of study treatment. Contraception requirements do not apply to participants in an exclusively same-sex relationship. Female participants should not donate eggs until 6 months after the last dose of study treatment.

8) Male participants must be surgically sterilized (performed at least 6 months prior to Baseline [Day 1] visit and documented to no longer produce sperm); or from signing of informed consent until at least 6 months after the last dose of study treatment, agree to use highly effective methods of contraception as described in [Section 5.3](#) with female partners of childbearing potential during the study and must also agree not to donate sperm during this period.

5.2 Exclusion Criteria

Participants fulfilling any of the following exclusion criteria are not eligible for entry into the study:

- 1) Severe cardiovascular, pulmonary, renal, autoimmune and metabolic illness(es), or any other acute or chronic medical or psychiatric condition or laboratory abnormality that could increase the risk associated with study participation or could interfere with the interpretation of study results and, in the judgment of the investigator, would make the patient inappropriate for entry into the study.
- 2) History of clinically significant abnormal laboratory values, as determined by the principal investigator (PI), including but not limited to the following:
 - a) Alanine aminotransferase (ALT) or aspartate aminotransferase (AST) $\geq 2.5 \times$ upper limit of normal (ULN) at the Screening visit.
 - b) Total bilirubin above $1.5 \times$ ULN (unless the elevated bilirubin is related to confirmed Gilbert's Syndrome) at the Screening visit.
 - c) White blood cell count $< 3,000/\text{mm}^3$ ($< 3.0 \times 10^9/\text{L}$) at the Screening visit.

Note: If the test results meet the above criteria, a repeat test may be performed to determine eligibility.

- 3) Positive hepatitis B virus (HBV), hepatitis C virus (HCV), or human immunodeficiency virus (HIV) serology results at Screening visit as defined below:
 - a) HBV: Positive test for hepatitis B surface antigen (HBsAg), OR positive test for hepatitis B core antibody (HBcAb) with negative test for hepatitis B surface antibody (HBsAb)
 - b) HCV: Positive test for hepatitis C antibody
 - c) HIV: Positive test for HIV antibody
- 4) Evidence of active or latent TB as confirmed by the screening TB test.
- 5) History of untreated or inadequately treated TB infection.
- 6) Active infection requiring treatment with systemic antibiotics, antivirals, antifungals, antiparasitics or antiprotozoals at the Screening and the Baseline (Day 1) visit.
- 7) Active unstable (e.g., in an acute flare) skin conditions in addition to AD that would interfere with the assessment of AD based on the investigator's clinical judgement.
- 8) Use of topical treatments such as TCSs, TCIs, topical phosphodiesterase-4 inhibitors and topical janus kinase (JAK) inhibitors for AD within 2 weeks before the Baseline (Day 1) visit.
- 9) Use of phototherapy for AD with ultraviolet (UV) A or UVB or regular use of a tanning booth within 4 weeks before the Baseline (Day 1) visit.
- 10) Use of non-biologic systemic (oral or injectable) agents including conventional immunosuppressants or immunomodulators (e.g., corticosteroids, methotrexate, cyclosporin, tacrolimus, mycophenolate mofetil, azathioprine, JAK inhibitors), and other approved drugs with potential immunosuppressive effects, within 4 weeks or 5 half-lives, whichever is longer, prior to the Baseline (Day 1) visit.
- 11) Use of biologic therapy including approved and investigational agents (e.g., mAbs against IL-13 or IL-4 alpha, investigational mAbs against IL-31 or IL-31 receptor) within 3 months or 5 half-lives, whichever is longer, prior to the Baseline (Day 1) visit.
- 12) Receipt of a live (including live attenuated) vaccine within 2 months prior to the Baseline (Day 1) visit (participants must agree to avoid live [including live attenuated] vaccination during study treatment and within 3 months thereafter).
- 13) Any known hypersensitivity to any component of study treatment or other biologics (e.g., mAbs, fusion proteins)
- 14) Malignancy or a history of malignancy (exception: fully-treated skin basal cell or non-metastatic squamous cell carcinomas; or cervical carcinoma in situ with no evidence of recurrence within 5 years) prior to the Screening visit.

- 15) Planned major surgical procedure during the study.
- 16) Participation in another research study involving an investigational product within 3 months prior to the Baseline (Day 1) visit.
- 17) Women who are pregnant or nursing. All female participants with reproductive potential must have a negative pregnancy test prior to starting study treatment.

5.3 Contraception Recommendations

A female who is permanently surgically sterile or postmenopausal is not considered to be a female of childbearing potential and is not required to follow contraception recommendations.

Surgically sterile is defined as:

- Bilateral oophorectomy (surgical removal of both ovaries); or
- Bilateral salpingectomy (surgical removal of both fallopian tubes); or
- Hysterectomy (surgical removal of uterus)

Postmenopausal is defined as no menses for 12 months without an alternative medical cause. A high follicle stimulating hormone level in the postmenopausal range may be used to confirm a postmenopausal state in women not using hormonal contraception or hormonal replacement therapy.

A female who does not meet the definition of postmenopausal or permanently surgically sterile or is postmenarchal or pubertal but has not yet had menses is considered of childbearing potential and is required to practice at least one of the following highly effective methods of birth control consistently from signing of informed consent until 6 months after the last dose of study treatment.

- Combined (containing estrogen and a progestogen) hormonal contraception (oral, intravaginal, transdermal, injectable) associated with the inhibition of ovulation.
- Progestogen-only hormonal contraception (oral, injectable, implantable) associated with inhibition of ovulation.
- Bilateral tubal occlusion/ligation.
- Vasectomized partner(s) provided that the vasectomized partner has received medical confirmation of the surgical success and is the sole sexual partner of the female trial participant of childbearing potential.
- Intrauterine device.
- Intrauterine hormone-releasing system.
- True abstinence (if acceptable per local requirements): Refraining from heterosexual intercourse when this is in line with the preferred and usual lifestyle of the participant. Periodic abstinence

(e.g., using calendar, ovulation, symptothermal, postovulation methods) and withdrawal are not acceptable.

The above-mentioned definition for true abstinence also applies to male participants. Contraception requirements do not apply to participants in an exclusively same-sex relationship.

5.4 Screen Failures

Screen failure occurs when a participant who has consented to participate in the clinical study is not subsequently assigned to study intervention or enrolled in the study. A minimal set of screen failure information is required to ensure transparent reporting of screen failure participants to meet the CONSORT publishing requirements and to respond to queries from regulatory authorities. Minimal information includes demography, screen failure details, eligibility criteria, and any SAE.

The participant who does not meet the criteria for participation in this study (screen failure) may be rescreened. A participant can only be rescreened once. If a participant fails screening for reason(s) which, in the opinion of the investigator, may be changed to make the participant eligible, the participant may be rescreened one time. In this case, the participant will re-sign the informed consent document and have all screening procedures performed. If a participant had a complete initial screening evaluation including TB test, the test will not be repeated for rescreening, provided the conditions noted in [Section 5.1](#) and [Section 5.2](#) of the protocol are met with no changes in the participant's medical history that warrant retesting, and no more than 90 days have passed. The investigators are encouraged to contact the medical monitor to confirm if subjects should or should not be rescreened.

6 STUDY INTERVENTION(S) AND CONCOMITANT THERAPY

6.1 Treatment Assignment

Cohort 1 will be an open label design. Approximately 15 consented participants who meet all eligibility criteria will be enrolled in Cohort 1 to receive three IV infusions of IMG-007 300 mg over 4 weeks. Participants will be assigned a unique enrollment number in ascending numerical order. Enrollment numbers are allocated sequentially in the order in which the participants are enrolled.

Cohort 2 will be a randomized, double-blind and placebo-controlled design. Approximately 40 consented participants who meet all eligibility criteria will be randomized at Baseline (Day 1) in a 3:1 ratio to receive three IV infusions of IMG-007 [REDACTED] or matching placebo over 4 weeks. Randomization will be stratified by disease severity (IGA 3 or IGA 4) at Baseline. Participants will be assigned a randomization number in ascending numerical order. The randomization number encodes the participant assignment to either IMG-007 [REDACTED] or matching placebo. Randomization will be performed using an interactive voice response system (IVRS) or interactive web response system (IWRS) software.

6.2 Treatment Blinding

Cohort 1 will be an open label design.

Cohort 2 will be a double-blind design. The study will be unblinded to select personnel from the Sponsor and/or participating CROs which will be specified in a separate document for the Blinding

Plan and Unblinding Process. The SRC team may receive unblinded data for safety evaluation. The study will remain blinded (except for emergency unblinding) for all other study personal/consultants, investigative site personnel, and study participants until the pre-specified unblinding to perform the primary analysis ([Section 11.3.7](#)). After the primary analysis, investigator, and study staff (except for emergency unblinding) as well as CRO staff (except for emergency unblinding) will remain blinded until the end of the study. To maintain the blind, all participants will receive three IV infusions over 4 weeks. Results from the PK and anti-drug antibody (ADA) measurements will not be communicated to the sites.

At initiation of the study, the study site will be instructed on the method of breaking the blind for individual participant in case of emergency. Blinding codes should only be broken for individual participants in emergency situations for reasons of participant's safety, or where knowledge of study treatment allocation will impact on the participant's medical management. The IVRS/IWRS will be used to provide the treatment assignment to the investigator. If unblinded, only the investigator and the affected participant will know the treatment assignment. Whenever possible, the investigator should inform the medical monitor when breaking the blind. When the blinding code is broken, the reason must be fully documented and entered in the case report form (CRF). In such cases, treatment with the investigational product must be stopped ([Section 6.10.1.1](#)) and the Medical Monitor must be contacted immediately to determine whether the participant should be withdrawn from study treatment.

6.3 Investigational Product Supply

IMG-007 and placebo will be supplied by the Sponsor and labeled appropriately as the investigational product for this study. The investigator must ensure that the investigational product will be used only in accordance with the protocol.

The investigational product administered in this clinical trial is IMG-007 protein provided as active substance (nominal 50 mg/mL) in a 2R Type I glass vial with a 13-mm rubber stopper integrated into a plastic cap. The IMG-007 vials are to be stored at 2 to 8°C and protected from light. The investigational product will be prepared for the desired dose and diluted with isotonic saline solution (0.9% sodium chloride marketed product) and to be administered via IV infusion.

The matching placebo of IMG-007 is identical in formulation to that of IMG-007 minus the active ingredient. The matching placebo is to be stored at 2 to 8°C and protected from light. The placebo will be prepared for the desired dose and diluted with isotonic saline solution (0.9% sodium chloride marketed product) and to be administered via IV infusion.

The isotonic saline solution (0.9% sodium chloride marketed product) to be used for dilution can be stored at room temperature.

For detailed instructions for storage, handling, reconstitution, and administration of all study treatments, please refer to the Investigational Medicinal Products Manual.

6.3.1 Packaging and Labeling

The labeling for IMG-007 and the matching placebo will be in accordance with Good Manufacturing Practice and Good Clinical Practice (GCP) and any other local regulatory requirements.

Each vial of IMG-007 or placebo will have a one-piece/booklet label attached to it and will be placed in a carton. The carton will have a one-piece/booklet label attached with the following information included: Sponsor name and address, protocol number, investigational product name, dosage form and strength (where applicable), amount of investigational product per container, lot/batch number, expiration date, medication identification number, storage conditions and any required caution statement(s) and/or regulatory statements, as applicable.

The investigational product for Cohort 1 and Cohort 2 will be packed and labeled separately. For Cohort 1, investigational product with open label for IMG-007 will be provided. For Cohort 2, investigational product with blinded label for IMG-007 or placebo will be provided. Additional information may be included on the label as applicable per local regulations. Both the vial label and the carton label will include a medication number.

6.3.2 Preparation and Dispensing

The investigational product will be prepared for the desired dose and diluted with isotonic saline solution (0.9% sodium chloride marketed product) to be administered via IV infusion.

Refer to the Investigational Medicinal Products Manual for details about preparation and dispensing of IMG-007 and placebo.

6.4 Dosing and Administration

IMG-007 should be administered via IV infusion.

Participants in Cohort 1 will receive IMG-007 300 mg on Day 1, Day 15, and Day 29.

Participants in Cohort 2 will receive IMG-007 █ or matching placebo on Day 1, Day 15, and Day 29.

Participants will receive the study treatment at the study site. The investigational product will be diluted with normal saline and administered by continuous IV infusion over approximately 60 minutes at slower rate during the first 15 minutes. Participants will be closely monitored at the study site for a minimum of 1 hour after completion of each infusion or until any AEs observed during observation have resolved or stabilized, whichever is longer. Study sites should have access to equipment or facilities for the management of potential hypersensitivity reactions.

It is anticipated that the infusion should be completed within 4 hours after preparation of the infusion solution. Refer to the Investigational Medicinal Products Manual for details about dosing and administration of IMG-007 and placebo.

6.5 Dose Modifications and Delays

Dose modification of the study treatment is not allowed. Any inadvertent dose modifications should be discussed with the medical monitor. Dosing should occur as close as possible on the allocated visit day and within the visit windows specified in the SoA ([Table 1](#)), except that dosing may be interrupted due to reasons stated in [Section 6.10.1.2](#). If a dose is not administered on schedule due to a visit occurring beyond the visit window specified in the SoA or dose interruption for reasons stated in [Section 6.10.1.2](#), the dose may be administered if it is no later than 5 calendar days after the allocated

visit day (a 10-calendar day delay will be allowed for the last dose at Week 4) specified in the SoA. Otherwise, the dose will be considered missed, and dosing will resume with the next scheduled dose per the SoA.

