7.3 Analysis Visit Window

[figure not shown]
For summaries that include data collected over multiple visits, where appropriate, the data will be summarized by analysis visit window. If there are multiple measurements within a scheduled visit window (refer [Appendix 12.6](#)), the closest measurement to the scheduled timepoint of the visit will be used in the analysis. If there are two observations which have the same difference in days to the planned day, but which are not measured on the same day, the later value will be selected. If there is more than one observation on the same day then;

- Latest value will be considered in all cases except for vital signs, ECG.
- Average value will be considered in cases of continuous vital signs and ECG parameters.
- The worst value will be considered for ECG interpretation.

All measurements will be presented in the listing.

[figure not shown]

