12.6 Analysis Visit Window

Analysis Visit	Target Day	Group 1	Group 2	Group 3*	Group 4	Group 5	Group 6
Baseline	1	Up to day 1	-	Up to day 1			
Week 1	8	2-11	2-11	-	-	-	-
Week 2	15	12-22	12-22	2-22	2-22	-	2-22
Week 4	29	23-36	23-36	23-57	23-43	2-43	23-43
Week 6	43	37-50	37-50	-	-	-	-
Week 8	57	51-64	51-64	-	44-64	44-64	44-64
Week 12	85	65-92	65-92	58-127	65-92	65-92	65-92
Week 16	113	93-120	93-120	-	93-120	93-120	93-120
Week 20	141	121-148	121-148	-	121-148	121-148	121-148
Week 24	169	149-172	149-172	128-172	149-172	149-172	149-172

Group 1: Vital signs, Physical examination, Adverse events, Prior and concomitant therapies, Hematology, blood chemistry, EASI, IGA, SCORA, Itch and sleep quality NRS, PGIS, PK sampling, Receptor occupancy and TARC.

Group 2: PGIC

Group 3: Urinalysis

Group 4: Pregnancy test

Group 5: DLQI.

Group 6: ADA sampling

*Use group 3 for ECG and TB assessment by removing week 2 and week 4 and changing the Week 12 window from '58-127' to "2-127".

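### A permitted third infusion on Days 37-39 falls in the SAP's Week 6 window for Groups 1 and 2, so an observed Week 4 record can drop out of by-visit analyses or be relabelled

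*Protocol*

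**What the plan says.** Protocol 6.4 fixes the dosing days: "Participants in Cohort 1 will receive IMG-007 300 mg on Day 1, Day 15, and Day 29". Protocol 6.5 then allows delays. It names two routes to a late dose: "If a dose is not administered on schedule due to a visit occurring beyond the visit window specified in the SoA or dose interruption". For doses in general, "the dose may be administered if it is no later than 5 calendar days after the allocated" visit day; for the third, "a 10-calendar day delay will be allowed for the last dose at Week 4".

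SAP 12.6 sets analysis windows by data type. The Week 4 row for Groups 1 and 2 reads "Week 4 29 23-36 23-36", and Week 6 for those groups runs from Day 37 to Day 50. Across Groups 1 to 6 the Week 4 windows are "23-36 23-36 23-57 23-43 2-43 23-43". The first group is the large one: "Group 1: Vital signs, Physical examination, Adverse events, Prior and concomitant therapies, Hematology, blood chemistry, EASI, IGA", followed by SCORAD, itch and sleep NRS, PGIS, PK, receptor occupancy and TARC. Group 2 is PGIC.

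Where a window holds several measurements, SAP 7.3 says that "the closest measurement to the scheduled timepoint of the visit will be used in the analysis". Ties on different days go to the later value, and listings show everything. No exception for a delayed dosing visit appears in SAP 7.3 or 12.6.

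**The concern.** The dosing allowance in the protocol runs three days past the end of the SAP's Week 4 window for most of the efficacy, PK, PD and by-visit safety data. A visit can be fully compliant as the Week 4 dosing visit and still be classed as Week 6. There it competes with the real Week 6 visit and normally loses.

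The consequences differ by analysis:

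- **Continuous endpoints.** SAP 6.8.1 imputes nothing for the main efficacy analysis, so the MMRM loses a Week 4 observation that was made.
- **Key binary endpoints.** SAP 6.8.2.2 applies LOCF to missing visits, so an earlier status replaces the observed Week 4 status.
- **By-visit vital signs, laboratory, PK and RO summaries.** Records from the day of the third infusion can leave the Week 4 row.

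The groups also disagree with each other. For one visit on Day 38, the ADA sample stays in Week 4 (Group 6) while the PK sample moves to Week 6 (Group 1).

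**Working it through.** **Inputs.** Third dose due Day 29 (Protocol 6.4). Permitted delays of 10 days for the third dose and 5 days otherwise (Protocol 6.5). Visit tolerance ±3 days (Protocol Table 1). Windows from SAP 12.6. Closest-to-target and later-if-tied rules from SAP 7.3. Thirteen participants enrolled (Protocol 4.1).

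**Step 1: reproduce the SAP's limit.** Midpoints between neighbouring target days give the Week 4 window for Groups 1 and 2: (15 + 29)/2 = 22, so it starts on Day 23; (29 + 43)/2 = 36, so it ends on Day 36. The same rule gives the other Week 4 upper limits: Group 3, (29 + 85)/2 = 57; Groups 4-6, (29 + 57)/2 = 43. The limits match target-day spacing; the dosing allowance does not enter.

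**Step 2: latest permitted doses.** Third dose: 29 + 10 = Day 39, which is 3 days past Day 36. Second dose: 15 + 5 = Day 20, inside its 12-22 window. Only the third dose is affected.

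**Step 3: where each third-dose day falls (Days 26-39).**

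| Third-dose day | Delay | Groups 1 and 2 | Groups 3 to 6 |
|---|---|---|---|
| 26-36 | up to 7 days | Week 4 | Week 4 |
| 37-39 | 8-10 days | Week 6 | Week 4 |

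**Step 4: competition with an in-window Week 6 visit (Days 40-46).** Distance of the dosing visit from Day 43: 6, 5 and 4 days for Days 37, 38 and 39. Distance of the Week 6 visit: 0 to 3 days. The dosing visit loses in all 3 × 7 = 21 combinations.

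**Step 5: when the dosing visit would be kept as Week 6.** It must be strictly closer to Day 43, because ties go to the later record.

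| Dosing visit | Distance | Kept over a Week 6 visit on |
|---|---|---|
| Day 37 | 6 | Day 50 |
| Day 38 | 5 | Days 49-50 |
| Day 39 | 4 | Days 48-50 |

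It is also kept if no Week 6 visit exists in the window. All these cases lie outside the ±3-day schedule.

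**Step 6: the two routes to a late dose.** If the whole visit was late, Week 4 has no Group 1 or 2 record. If only the dose was held and the Week 4 assessments were done on time, the on-time scores stay in Week 4. The vital signs and PK/RO samples from the later infusion day can still be displaced.

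**Step 7: size.** One affected participant is 1/13 = 7.7% of Week 4.

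**Step 8: check of the proposed windows.** With Week 4 = 23-39 and Week 6 = 40-50, every permitted third-dose day (26-39) maps to Week 4 and every in-window Week 6 visit (40-46) maps to Week 6, without overlap.

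**The case against.** A midpoint window is a standard convention, and by calendar distance an EASI on Day 39 is nearer to Day 43 (4 days) than to Day 29 (10 days). That is true. But a score taken before the third infusion reflects two doses, and the present rule usually discards it rather than using it as Week 6.

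A reader might infer that the primary safety result is compromised. The documents do not support this. The primary endpoint is TEAE incidence; SAP 4.6.1 counts all AEs in the treatment and follow-up periods, and SAP 6.9.1 summarises them by participant, not by window. Laboratory CTCAE tables use the worst grade (SAP 6.9.2). Listings keep every measurement, so nothing is lost from the record.

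A reader might also infer that an end-of-infusion peak will be reported as a Week 6 concentration. This is possible but not established. SAP 7.3 applies windows only where suitable, and PK has distinct pre-dose and end-of-infusion samples (SAP 4.7). Read without regard to timepoint, the same-day rule would discard every pre-dose PK sample on every on-schedule dosing day, which can hardly be intended. What stands is that the SAP does not say how infusion-day timepoints are handled, so the size of any PK distortion cannot be stated.

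The reach is also narrow. It takes an 8-10-day delay, and perhaps nobody had one. The Week 12 EASI endpoint is touched only through one missing repeated measure per affected participant. Finally, SAP Section 1 cites protocol Version 6.0 of 5 February 2024, whereas the protocol at hand is dated 14 June 2024; whether Version 6.0 had the 10-day allowance cannot be seen.

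**Conclusion.** The mismatch is real and follows from calendar arithmetic: Day 39 against Day 36, for Groups 1 and 2 only. A compliant dosing visit on Days 37-39 is displaced by any in-window Week 6 visit. With a wholly late visit, an observed Week 4 value is then missing from by-visit summaries and the MMRM, or overwritten by LOCF in the key binary endpoints. With a held dose, only infusion-day records are at risk. Reporting the dosing-day record as Week 6 needs a missed or very late Week 6 visit.

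The effect is 7.7% of Week 4 per affected participant and zero if no one was dosed on Days 37-39. This assumes that the windows are applied by study day as written and that the redacted text contains no exception. It is a local defect in visit labelling, not a threat to the primary or secondary conclusion. The protocol and SAP passages need to be reconciled; no view is taken on the dosing rule itself.

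**What to change.** Two changes in SAP 7.3 and 12.6, with no change to dosing:

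1. Assign infusion-day records (vital signs, pre-dose and end-of-infusion PK and RO) to the nominal visit and timepoint of the infusion they belong to, whatever the study day. Keep them separate from any on-time Week 4 record. Widening the window alone is not enough: with a held dose, Day 29 and Day 39 records would both sit in Week 4, and the closest-to-target rule would drop the Day 39 ones.
2. For the other Group 1 and 2 assessments, set Week 4 to Days 23-39 and Week 6 to Days 40-50, so that a wholly late dosing visit stays in Week 4.

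The cost is two limits in each of two columns and one or two sentences. The downside is that an unscheduled, non-dosing assessment on Days 37-39 would be labelled Week 4.

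The sponsor can check the third-dose dates of the 13 participants directly. Enrolment ended on 31 January 2024; if that was the last Day 1, Day 39 is 38 days later, 9 March 2024, before SAP Version 2.0 of 17 May 2024. If no one was dosed on Days 37-39, a sentence saying so closes the point.
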